7.3 Medical history

Medical history still ongoing at enrolment or ended prior to enrolment will be listed together for the Full Analysis Set. Medical history will be coded according to Medical Dictionary for Regulatory Activities (MedDRA® version 22.0 (or later)) and will be classified as follows

- Previous medical conditions: medical conditions that stopped prior to start of treatment
- Ongoing (concomitant) medical conditions: medical conditions still present after start of treatment

The frequency of diseases recorded from medical history will be presented after classification into previous and concomitant conditions by system organ class (SOCs) as well as the frequencies of preferred terms (PT) within each SOC. If subjects have more than one disease within an SOC or PT they will be counted only once for the respective SOC or PT.

8 Exposure and Compliance

Exposure and compliance data will be summarized and listed by subject based on Full Analysis Set. A listing of drug administration will be created and will include the date and time of administration.

8.1 Treatment groups

Treatments will be labelled as follows:

- LT5001 drug product
- Placebo

For the FAS, subjects will be assigned to the treatment groups they were randomised to and for the SAS, PP and PKAS to the treatment they actually received.

In case that a subject received different treatments due to mix-up the subject will be assigned as follows in the SAS:

- In case of mixture of placebo and active treatment the subject will be assigned to the respective active treatment.

Deviations from the randomised treatment will be presented in the protocol deviation listing, see section 6.3 Protocol deviations.

8.2 Dosage

QMS Document Name: Statistical Analysis Plan	Page 15 of 33
QMS No (include version ref): STF-015-GL.02	Document date: 09JUL2019
CONFIDENTIAL	

Descriptive statistics for the actual total dose will be presented overall and by treatment group for the FAS.

8.3 Treatment duration

The treatment duration will be calculated in days as:

Treatment duration (days) = (date of last application – date of first application) + 1

If the date of first application of study medication is missing, it will be assumed to be identical to the date of randomisation.

Descriptive statistics for the treatment duration will be presented.

8.4 Compliance

Details regarding dosing, including the dose administered and the date and time of dosing, will be recorded.

Formulation of study drug is ointment and it will be applied to the skin to treatment.

The number of tubes applied will be the sum of the number of “Drug Used (AM)” and “Drug Used (PM)” from the eCRF “Treatment of Study Medication” form when “Yes” are selected.

Percent compliance will be derived as the number of tubes actually applied divided by the number of tubes expected to be applied, expressed as a percent.

- Treatment compliance:

(The actual number of tubes applied in each treatment group / Expect total tubes applied in each treatment group)*100%

If the subjects do not feel itchy, drug used will be recorded as “not applicable” in CRF. In this case, it will be excluded from calculating of the compliance.

- Treatment compliance by categories (<80%, 80%-100%)

9 Previous and Concomitant Therapies/ Anti-itch medications

Prior and concomitant medications are coded according to the World Health Organization drug dictionary (WHO-Drug latest version) and stored with ATC codes and generic names.

Prior and concomitant medication will be recorded on the eCRF (Form: Concomitant Medications). Prior medication is defined as any medication or device other than the study drug within 30 days prior to the Screening Visit. Concomitant medication is any medication other than the study drug that is taken from the time of study entry (date of informed consent signed) to the end of study. Upon entering the study, each subject will be instructed to report the use of any medication to the investigator.

The summary tables by treatment groups and overall for prior and concomitant medication will be provided detailing the number and percentage of subjects by anatomical main group (ATC Level 2) and preferred term using World Health Organization Drug Dictionary (WHO-DD) Enhanced latest version

QMS Document Name: Statistical Analysis Plan	Page 16 of 33
QMS No (include version ref): STF-015-GL.02	Document date: 09JUL2019
CONFIDENTIAL	

Anti-itch medications are identified as medications where “Yes” is checked on the Previous or Concomitant Medications CRF page to the question “Is the medication anti-itch?” The prior and concomitant medication summaries described above will be repeated for the anti-itch medications, presented by generic name.

10 Efficacy

The FAS will be used for efficacy endpoint evaluation. Efficacy analysis will be repeated on the PP Population.

The following efficacy endpoints will be assessed by Part of study.

Part A:

- Change in mean Worst Itching Intensity using NRS from baseline to the end of Week 4.
- Proportion of patients reduced NRS from baseline with respect to weekly mean of the daily 24-hour Worst Itching Intensity NRS score from baseline to the end of Week 4.
- Change from baseline in 5-D Itch Scale score at the end of Week 4.
- Change from baseline in total Skindex-10 Scale score at the end of Week 4.

Part B:

- Change from baseline to the end of Week 8 in mean Worst Itching Intensity using NRS (Primary endpoint in Part B)
- Proportion of patients reduced NRS from baseline with respect to the weekly mean of the daily 24-hour Worst Itching Intensity NRS score from baseline to the end of Week 8.
- Change from baseline in 5-D Itch Scale score at the end of Week 8.
- Change from baseline in total Skindex-10 score at the end of Week 8.

The efficacy analysis will be based on a linear mixed effect model for repeated measurements (MMRM) using all the longitudinal observations at each post-baseline visit through the last visit.

To select an appropriate covariance model, covariates of baseline itch and status of prior anti-itch medication use

Proportion of patients improved NRS from baseline (2-points, 3-points, or 4-points) was evaluated at each time point compared between treatment group using logistic regression analysis.

10.1 Primary efficacy analysis

Numerical Rating Scale (NRS)

Numerical Rating Scale (NRS), an unidimensional scale, which may be the most widely used is a validated measurement of UP intensity in HD patients. Patients can be asked to rate their itch intensity from 0 (“no itch”) to 10 (“worst imaginable itch”) with the NRS.

Patients will be recorded the daily Worst Itching Intensity in the patient diary and review will be conducted in each visit.

QMS Document Name: Statistical Analysis Plan	Page 17 of 33
QMS No (include version ref): STF-015-GL.02	Document date: 09JUL2019
CONFIDENTIAL	

The weekly mean of the 24-hour Worst Itching Intensity NRS score will be defined as the sum of the daily Worst Itching Intensity NRS scores reported during a specific week during the Treatment Period (e.g., Days 1 to 7, Days 8 to 14, Days 15 to 21) divided by the number of days with non-missing scores for that week. If the daily worst itching score is missing for >3 days during a specific week, the corresponding weekly mean worst itching score will be set to missing. Additionally, subjects who discontinue treatment but continue on study and report NRS scores will have their NRS scores censored following discontinuation of treatment; missing data rules will apply to these censored values as though they had missing values/ dropped out from the study entirely.

The baseline score was defined as the average of the daily 24-hour Worst Itching Intensity NRS scores reported over the 7-day Run-in Period. As defined in the protocol, to be randomized, subjects had to report at least 6 non-missing Worst Itching Intensity scores from the start of the 7-day Run-in Period and mean NRS score >4 to qualify.

As a continuous variable, the data value of NRS on the each visit will be derived based on the average value of the values that each subjects had recorded from the previous visit day to next visit day. Change from baseline in NRS will be summarized as descriptive statistics by overall subjects and treatment group for Part A and Part B. For Part B, it will further be analyzed using mixed-effect model repeated measure analysis of covariance to compare the treatment group considering covariates (baseline itch and prior anti-itch medication use). Additionally, treatment group, time, an interaction term for treatment group and time will be included into the model as factors. The model will be used to estimate the NRS at end of treatment. Least square means and their standard errors, along with their 95% confidence interval (CI) of treatment difference will be calculated.

To perform MMRM, SAS programming will be used as follows.

```
proc mixed data= dataset ;
  class treatment time subject prior_med;
  model NRS=treatment time treatment*time baseline_itch prior_med /solution ddfm=kr;
  lsmeans treatment*time/cl pdiff;
  repeated time/type=un subject=subject;
run;
```

By using derived NRS at the timepoint, the subjects reduced NRS from baseline (≥ 2 -points, ≥ 3 -points, ≥ 4 -points) to each time point will be categorized. It will be summarized by frequency and percentage of subjects. For Part A and B, logistic regression analysis will be further performed to compare treatment group differences at each time-point, providing with odds ratio and 95% CI.

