10.7 Efficacy Analysis

The efficacy of LT5001 drug product will be assessed via the following:

Part A:

- Change in mean Worst Itching Intensity using NRS.
- Proportion of patients reduced NRS from baseline with respect to weekly mean of the daily 24-hour Worst Itching Intensity NRS score from baseline to the end of Week 4.
- Change from baseline in 5-D Itch Scale score at the end of Week 4.

CONFIDENTIAL

- Change from baseline in total Skindex-10 Scale score at the end of Week 4.

Part B:

- Change in mean Worst Itching Intensity using NRS.
- Proportion of patients reduced NRS from baseline with respect to the weekly mean of the daily 24-hour Worst Itching Intensity NRS score from baseline to the end of Week 8.
- Change from baseline in 5-D Itch Scale score at the end of Week 8.
- Change from baseline in total Skindex-10 score at the end of Week 8.

Mixed-effect model repeated measures analysis of covariance will be applied to compare the treatment groups for efficacy endpoints (i.e. change of NRS, change from baseline in 5-D Itch Scale, change from baseline in total Skindex-10), with baseline itch and prior anti-itch medication use as covariates, and patient as a random effect.

Proportion of patients improved NRS from baseline (2-points, 3-points, or 4-points) was evaluated at each time point compared between treatment group using logistic regression analysis.

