5.5 Covariates and Strata

In Mixed-effect model repeated measures analysis, baseline itch and prior anti-itch medication use will be considered as covariates for efficacy endpoints in Part B.

Strata is not applicable in this study.

6 Subject Accounting and Disposition

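### The Part B responder logistic regression names no covariates, unlike the other Part B efficacy models; adding baseline NRS and prior anti-itch medication use is a cheap improvement

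*SAP*

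**What the plan says.** Three places describe the responder analysis, and none names a covariate.

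- Protocol Section 10.7: the proportions improving by 2, 3 or 4 points are "compared between treatment group using logistic regression analysis".
- SAP Section 10, overview of efficacy: the same endpoint "was evaluated at each time point compared between treatment group using logistic regression analysis".
- SAP Section 10.1: for Parts A and B, "logistic regression analysis will be further performed to compare treatment group differences at each time-point", with the odds ratio and its 95% CI to be reported.

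The covariates appear elsewhere, attached to the mixed model.

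- SAP Section 5.5: "In Mixed-effect model repeated measures analysis, baseline itch and prior anti-itch medication use will be considered as covariates for efficacy endpoints in Part B". The same section says that there are no strata.
- SAP Section 10.1, code for the continuous NRS endpoint: "model NRS=treatment time treatment*time baseline_itch prior_med /solution ddfm=kr".
- Protocol Section 10.7, for the NRS, 5-D Itch and Skindex-10 changes: a mixed model "with baseline itch and prior anti-itch medication use as covariates, and patient as a random effect".
- SAP Section 10.2 repeats both covariates for the 5-D Itch and Skindex-10 mixed models.

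No code is given for the logistic model. Both variables are available: baseline NRS is the run-in mean (SAP Sections 5.3 and 10.1), and anti-itch medication is flagged on the medication page of the CRF (SAP Section 9).

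**The concern.** The responder proportion is the only Part B efficacy comparison with no stated adjustment, yet it is built from the same diary scores as the primary endpoint. Response is an absolute drop from a baseline that varies from just above 4 up to 10. If patients with higher baselines tend to drop further, baseline carries information about who responds. A treatment-only model does not use that information, and it does not correct for chance imbalance between arms.

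At stake are some power and consistency with the primary model. There is also a pre-specification gap. An adjusted and an unadjusted odds ratio estimate different quantities, and the text does not say outright which is meant. That choice stays open across three thresholds and every time point, with no multiplicity adjustment planned (SAP Section 5.4).

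**Working it through.** There is no plan figure to reproduce: both documents say that no formal sample size calculation was made, and neither gives an effect size, SD or responder rate.

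**Step 1. Relative size of a fixed drop.** Inputs from the documents: entry requires mean NRS above 4, the scale runs from 0 to 10, and thresholds are 2, 3 and 4 points. Required reduction = threshold / baseline.

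| Baseline | 2 points | 3 points | 4 points |
|---|---|---|---|
| 4.1 | 49% | 73% | 98% |
| 5 | 40% | 60% | 80% |
| 6 | 33% | 50% | 67% |
| 8 | 25% | 38% | 50% |
| 10 | 20% | 30% | 40% |

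**Step 2. Chance imbalance without strata.** Standard error of the difference in baseline means, in SD units = √(2/n). Part B size differs between the documents (protocol 45 per arm, SAP 30 per arm), so both are used.

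- n = 30: √(2/30) = 0.258; 95% range ±1.96 × 0.258 = ±0.51 SD.
- n = 45: √(2/45) = 0.211; 95% range ±1.96 × 0.211 = ±0.41 SD.

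**Step 3. Effect on power.** This was a simulation with 2,000 trials per scenario and a Wald test at two-sided 5%. It compared treatment alone with treatment + baseline NRS + prior medication. All inputs are assumptions:

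- baseline normal with mean 6.5 and SD 1.5, truncated to above 4 and at most 10;
- placebo improvement 1.8 points at baseline 6.5, treatment effect 1.2 points, residual SD 1.8;
- half the patients on prior medication, with a 0.5-point effect;
- follow-up score limited to 0–10;
- slope of improvement on baseline 0, 0.3 or 0.6.

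Power, treatment-only → adjusted (%):

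| Per arm | Threshold | Slope 0 | Slope 0.3 | Slope 0.6 |
|---|---|---|---|---|
| 30 | 2 | 52.7 → 52.6 | 49.7 → 50.4 | 43.0 → 47.6 |
| 30 | 3 | 51.0 → 51.2 | 48.3 → 50.3 | 45.2 → 47.9 |
| 30 | 4 | 33.4 → 33.9 | 34.1 → 36.1 | 34.1 → 38.8 |
| 45 | 2 | 67.3 → 68.8 | 64.9 → 67.3 | 60.7 → 66.0 |
| 45 | 3 | 65.8 → 67.0 | 65.9 → 68.1 | 59.9 → 66.1 |
| 45 | 4 | 55.6 → 55.5 | 54.4 → 54.4 | 49.0 → 53.2 |

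By subtraction, the change is −0.1 to +1.5 points at slope 0, 0.0 to +2.4 at slope 0.3, and +2.7 to +6.2 at slope 0.6. The Monte Carlo standard error of a single power near 50% is √(0.5 × 0.5 / 2000) = 1.1 points, so the slope-0 changes are close to noise. A second simulation with the likelihood-ratio test, 3,000 trials per scenario and slopes 0.3 to 0.6 gave −1 to +6 points.

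**Step 4. Type I error and the odds ratio.** With no treatment effect (3-point threshold, 30 per arm), the Wald test rejected in 3.5–3.8% of trials unadjusted and 4.4–4.7% adjusted. The likelihood-ratio runs gave 4.6% against 4.8%, and 6.0% against 6.7%. Adjustment also moves the target: at the 3-point threshold with 30 per arm and slope 0.6, the median odds ratio was 2.75 unadjusted and 3.23 adjusted.

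**Step 5. Sparse data.** At the 4-point threshold with 30 per arm, separation or an inestimable odds ratio occurred in 0.8–2.3% of Part B trials. In Part A (12:6, slope 0.3) it occurred in 13% of trials at 2 points and 48% at 4 points.

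**The case against.** The strongest reply is that little is wrong. Randomisation makes the treatment-only test valid, and the rejection rates in Step 4 show no improvement from adjustment. A marginal odds ratio is a legitimate target for a simple responder comparison. The primary endpoint, from the same diary data, is already adjusted. Being listed first among the Part B secondary endpoints gives this one no formal weight, since there is no testing hierarchy. All of that stands, and it limits the point to precision and consistency.

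Several stronger readings are tempting, and the documents do not support them.

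- A reader might infer that the plan prescribes an unadjusted model. It does not say so. It is silent, and SAP Section 5.5 makes treatment-only the natural reading. An unfinished sentence about the two covariates sits just before the responder sentence in the SAP Section 10 overview. It follows the mixed-model sentence and does not assign them to the logistic model.
- A reader might infer that a low baseline rules out response. It does not: every eligible patient starts above 4, so even a 4-point drop is attainable. Whether it is harder to reach depends on how change relates to baseline, which the documents do not report. At slope 0, simulated 4-point response was about 20% at both low and high baseline. At slopes 0.3–0.6 it was 11–15% for baseline 6 or below and 29–40% for 7.5 or above.
- A reader might take prior medication as a proven predictor. The only support is its choice as a mixed-model covariate.

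The objection that adjustment is not entirely free is also right. It changes the meaning of the odds ratio and needs a rule for sparse data.

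**Conclusion.** The point holds as a cheap improvement. As written, the Part B responder comparison is most naturally treatment-only, while the other Part B efficacy comparisons adjust for two variables that the trial already collects. Naming those covariates is a better-specified method, but it does not correct a bias or an invalid test.

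The gain is about 0 to +6 percentage points of power, at 30 or 45 per arm and slopes of 0 to 0.6. The upper end needs the steepest assumed slope, and the gain almost vanishes if baseline and change are unrelated. These figures rest wholly on assumed effect, variability and slope. The floor arithmetic and the imbalance ranges rest only on the documents. The case for stating the model in advance does not depend on the power figures.

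**What to change.** In SAP Sections 5.5 and 10.1, state that each Part B responder logistic regression includes treatment, baseline mean Worst Itching NRS (continuous) and prior anti-itch medication use (yes/no). Add that a penalised (Firth) fit is used where a threshold or time point has sparse cells or separation, and define that trigger before unblinding. Keep the unadjusted responder proportions by arm as the descriptive summary, and label the odds ratio as conditional on the covariates.

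Do not extend the adjusted model to Part A; with 12:6 it would often be inestimable. For Part A, reconcile the logistic comparison in SAP Section 10.1 with SAP Section 10.2, which makes the Part A secondary endpoints descriptive and limits statistical comparisons to Part B.

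The cost is a line of SAP text, the matching code and the sparse-data rule. No new data are needed. The downsides are the conditional interpretation of the odds ratio and the need for a penalised fit at sparse thresholds.

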10.2 Secondary efficacy analyses

In Part A, the secondary efficacy endpoints will be summarized using descriptive statistics. Statistical comparisons will only be performed in park B using a two-sided test at a significance level of 5%, and 95% CI and a P-value will be reported in case of efficacy analysis.

5-D Itch Scale

The 5-D itch scale was developed as a brief but multidimensional questionnaire designed to be useful as an outcome measure in clinical trials. The five dimensions are degree, duration, direction,

QMS Document Name: Statistical Analysis Plan	Page 18 of 33
QMS No (include version ref): STF-015-GL.02	Document date: 09JUL2019
CONFIDENTIAL	

disability and distribution. The duration, degree and direction domains each included one item, while the disability domain had four items. All items of the first four domains were measured on a five-point Likert scale.

The five-point Likert scale are rated from 1 to 5 points. For disability domain, the highest score on any of the four items will be used. For the distribution domain, the number of affected body parts is tallied (potential sum 0–16) and the sum is sorted into five scoring bins: sum of 0–2 = score of 1, sum of 3–5 = score of 2, sum of 6–10 = score of 3, sum of 11–13 = score of 4, and sum of 14–16 = score of 5. The total score of 5-D itch will be the sum of the 5 domains, ranging from 5 to 25 points.

5-D itch scale will be assessed at Visit 1, Visit 5, Visit 7 in Part A and Visit 1, Visit 3, Visit 5, Visit 7, Visit 9 (End of study) in Part B. Baseline of 5D itch score will be assessed at Visit 1.

Change from baseline in 5-D Itch Scale score at week 4 in Part A and Week 8 in Part B (total score and score for each domain) will be summarized by treatment group and visit.

In Part A and B, mixed-effect model repeated measure analysis of covariance will be performed to compare the treatment group considering covariates (baseline itch and prior anti-itch medication use).

Skindex-10 scale

Skindex-10 consists of 10 questions used to evaluate how the patient's itch affects three important domains of quality of life.

The total score of skindex-10 scale is the sum of the numeric value of each answered question. The domain scores are sums of the following: disease domain (questions 1 to 3), mood/emotional distress domain (question 4 to 6), and social functioning domain (questions 7 to 10)

Skindex-10 scale will be assessed at Visit 1, Visit 5, Visit 7 in Part A and Visit 1, Visit 3, Visit 5, Visit 7, Visit 9 (End of study) in Part B. Baseline of Skindex-10 score will be assessed at Visit 1.

Change from baseline in Skindex-10 Scale at week 4 in Part A and Week 8 in Part B (total score and score for each domain) will be summarized by treatment group and visit. In part A and B, mixed-effect model repeated measure analysis of covariance will be performed to compare the treatment group considering covariates (baseline itch and prior anti-itch medication use)

11 Safety

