3.1 General description

Indication	Hemodialysis patients with moderate-to-severe pruritus
Design	This is a randomized, double-blind, placebo-controlled study containing two parts: part A will assess the safety, tolerability and PK with 4-week treatment, part B will assess safety and efficacy for 8-week treatment. Both parts will apply investigational drug in hemodialysis patients with moderate to severe of uremic pruritus.
Phase	1 (Part A) and 2 (Part B)
Study Site:	[REDACTED] [REDACTED]
Sample size	
Part A:
 
Approximately 20 subjects will be screened to achieve 18 subjects enrolled (LT5001 drug product: Placebo=12:6).
 
Part B:
 
Approximately 66 subjects will be screened to achieve 60 subjects enrolled (LT5001 drug product: Placebo=30:30).

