3.3 Randomisation, blinding and unblinding procedures

Subjects will be randomized into the study once they have completed screening and the Day -1 pre-dosing assessments and have satisfied all eligibility criteria.

Hemodialysis subjects with moderate-to-severe pruritus will be assigned random allocation number as the following ratio in each study part.

For Part A, patients will be randomized into a 2:1 ratio to receive LT5001 drug product or placebo. Thus, LT5001 group, the resulting allocated subjects will be 12 subjects. The placebo group will contain 6 subjects.

For Part B, patients will be randomized into a 1:1 ratio to receive LT5001 drug product or placebo. Thus, LT5001 group, the resulting allocated subjects will be 30 subjects. The placebo group will contain 30 subjects.

QMS Document Name: Statistical Analysis Plan	Page 9 of 33
QMS No (include version ref): STF-015-GL.02	Document date: 09JUL2019
CONFIDENTIAL	

The CRO will maintain the randomization code in a secure location with controls to prevent unauthorized access, including the computer program written to generate the randomization, randomization codes, program log, seed number used by the program, copy of the randomization plan along with approval documentation as appropriate, and the write protected electronic storage medium.

The site and CRO will name an unblinded statistician to provide the randomization code. Investigators, pharmacists, site staff, patients, CRO, and the Sponsor will remain blinded to individual patients' treatment assignment for the duration of the study until the study unblinding has been authorized.

In order to preserve the blind, study drug will be prepared and administered in a manner that masks the content for both the patient and staff member administering the drug.

4 Analysis Sets

Enrolled Population (ENR)

The enrolled population will include all patients who provided informed consent. Summary of screening failures and randomized patients will be displayed for ENR population.

Safety Analysis Set (SAS)

The SAS will include all patients who receive at least 1 dose of LT5001 drug product or placebo in Parts A and B. Patients will be analyzed according to the treatment they actually received.

The Safety Population will be used for all safety analysis (adverse events, clinical laboratory tests, vital signs, physical examinations and application site examination).

Full Analysis Set (FAS)

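### SAP 10.2 reserves statistical comparisons for Part B, yet SAP 10.1 and 10.2 also order Part A logistic and mixed-model comparisons, where 12 v 6 patients can leave an odds ratio with no finite value

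*SAP*

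**What the plan says.** SAP 10.2 opens with two rules. For Part A: "In Part A, the secondary efficacy endpoints will be summarized using descriptive statistics". For testing: "Statistical comparisons will only be performed in park B using a two-sided test at a significance level of 5" per cent, where park is plainly a typing slip for Part. In line with this, SAP 10.1 applies the mixed model for change in NRS to Part B, and SAP 5.5 mentions the two model covariates in connection with Part B.

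Other sentences order the opposite:

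- SAP 10.1, NRS responders at 2, 3 and 4 points: "For Part A and B, logistic regression analysis will be further performed to compare treatment group differences at each time-point", with an odds ratio and 95% CI.
- SAP 10.2, 5-D Itch: "In Part A and B, mixed-effect model repeated measure analysis of covariance will be performed", for the stated purpose of comparing treatment groups.
- SAP 10.2, Skindex-10: "In part A and B, mixed-effect model repeated measure analysis of covariance will be performed", for the same purpose.

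SAP 3.1 lists the responder proportion, 5-D Itch and Skindex-10 as Part A secondary endpoints. The opening of SAP 10 and Protocol 10.7 each list endpoints for both parts and then name the mixed model and the logistic regression without limiting either to Part B. SAP 2.1 declares the SAP consistent with the protocol. SAP 3.3 allots 12 Part A patients to LT5001, and "The placebo group will contain 6 subjects".

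**The concern.** An analyst cannot treat Part A as descriptive and also fit models to compare its arms. While both rules stand, either choice can be defended as following the SAP, and the choice can be made after the data are seen.

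The results will be read. SAP 13 says the interim analysis after Part A covers all data and follows this SAP. Protocol 5.1.1 includes itch results in the DSMB's review, after which the sponsor makes an unblinded decision about Part B.

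The logistic analysis has a further practical problem. With six placebo patients an empty cell is possible, and the odds ratio is then zero, infinite or undefined. The SAP names no exact, penalised or descriptive fallback, and SAP 5.4 plans no multiplicity adjustment.

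**Working it through.** **The texts side by side.** The responder, 5-D Itch and Skindex-10 endpoints are all secondary in Part A, so the descriptive rule in SAP 10.2 covers all three. Each is also the subject of a sentence ordering a group comparison in Part A. For 5-D Itch and Skindex-10, the conflict lies within SAP 10.2 itself. Change in NRS is not in conflict inside SAP 10.1, but the unrestricted opening of SAP 10 leaves it open there.

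**Chance of an empty cell in one fit.** The plan states no figure to reproduce. Inputs: 12 and 6 patients (SAP 3.1 and 3.3), and assumed responder rates pT (LT5001) and pC (placebo), because the documents give none. For a treatment-only model:

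- A = pT^12 + (1 − pT)^12 (LT5001 all or none respond)
- B = pC^6 + (1 − pC)^6 (placebo all or none respond)
- P(empty cell) = A + B − AB

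| LT5001 / placebo (assumed) | A | B | P |
|---|---|---|---|
| 30% / 10% | 0.0138 | 0.5314 | 0.538 |
| 50% / 20% | 0.0005 | 0.2622 | 0.263 |
| 50% / 30% | 0.0005 | 0.1184 | 0.119 |
| 60% / 40% | 0.0022 | 0.0508 | 0.053 |
| 50% / 50% | 0.0005 | 0.0313 | 0.032 |

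In these rows nearly all the risk comes from the six placebo patients. A very high LT5001 rate would also raise it: at 90% / 50%, A = 0.2824 and P = 0.305. The SAP names no covariates for the logistic model. Adding some would not remove a separation that treatment alone already produces.

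**Across the set of fits.** The three thresholds are nested, so one pair of rates cannot serve all of them, or every week. A simulation took 3 thresholds × 4 weeks = 12 fits. It assumed normal weekly NRS reductions with SD 2, within-patient correlation 0.7 and four mean profiles, with Week 4 mean reductions of 0.8 to 3.0 points on placebo and 1.8 to 3.5 on LT5001.

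| Week 4 mean reduction, placebo / LT5001 | Average share of 12 fits not finite | At least one of 12 | At least one of 3 at Week 4 |
|---|---|---|---|
| 0.8 / 1.8 | 52% | 98% | 76% |
| 1.8 / 2.8 | 33% | 92% | 44% |
| 2.5 / 3.5 | 21% | 82% | 29% |
| 3.0 / 3.0 | 13% | 68% | 24% |

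**When the odds ratio is finite.** With 6/12 v 2/6, OR = (6 × 4)/(6 × 2) = 2.0. The standard error of log OR is √(1/6 + 1/6 + 1/2 + 1/4) = 1.041, so the Wald 95% CI is 0.26 to 15.4. The narrowest interval possible at these sizes, from 6/12 v 3/6, has standard error √(1/6 + 1/6 + 1/3 + 1/3) = 1 and runs from 0.14 to 7.1.

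**Part B for scale.** At 20% / 10%, the same formula with the Part B arm sizes gives 4.4% for 30 v 30 (SAP) and 0.9% for 45 v 45 (protocol). At 40% / 20% it is about 0.1% or less with either size.

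**The case against.** The best defence is that only tests and p-values are reserved for Part B. The logistic sentence asks for an odds ratio and CI, not a p-value, and the two-sided 5% test is tied to Part B. Part A could then be read as estimation only. This softens the conflict for the logistic sentence but does not remove it: SAP 10.2 also calls these Part A endpoints descriptive, while the logistic and mixed-model sentences are expressly there to compare groups.

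A second defence is that little depends on it. Protocol 3.5 seeks only to explore potential efficacy in Part A, and Protocol 5.1.1 makes Part B depend on the dose being judged safe and well tolerated. No efficacy hurdle or alpha is attached to Part A. That stands, and it limits the consequence to possible over-reading of itch results.

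A reader might also infer more than the documents support:

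- That the odds ratio will usually fail at every threshold and week. Without responder rates this cannot be said; with both rates near 40% to 60%, a single fit fails only about 3% to 5% of the time.
- That SAP 5.5 bars the covariates from Part A. It links them to Part B but does not say only.
- That the Part A mixed models cannot be fitted. The empty-cell argument does not apply to them, and no failure rate has been shown.

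**Conclusion.** Wrong as written, and it should be corrected before Part A is analysed. The contradiction rests on the text alone and holds whatever the responder rates.

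The size of the estimability problem is conditional on assumed rates and a treatment-only model: 3% to 54% per fit over the five pairs tabulated. Among those pairs it is frequent only where placebo response is about 20% or less. Across the full set of thresholds and weeks, at least one non-finite odds ratio is likely under all four simulated profiles, though that result depends on the assumed means, SD and correlation.

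**What to change.** - In the logistic sentence of SAP 10.1 and the two mixed-model sentences of SAP 10.2 (5-D Itch, Skindex-10), strike the reference to Part A so that each applies to Part B only.
- Add the same limit to the mixed-model and logistic statements at the opening of SAP 10. Otherwise the conflict survives there.
- Record in SAP 2.1 that Part A is not modelled, as a departure from Protocol 10.7. The present limit of the NRS-change model to Part B belongs in the same entry.
- For Part A, report responder counts by arm and means with SDs, without p-values. Exact (Clopper-Pearson) 95% intervals are one option, and they stay defined with an empty cell: 0 of 6 gives 0 to 1 − 0.025^(1/6) = 0.46.

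If the sponsor prefers to stay closer to Protocol 10.7, the alternative is to label the Part A comparisons exploratory, without p-values, specify an exact or Firth fallback for empty cells, and reword the opening of SAP 10.2 to match.

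The main fix costs SAP wording and a declared departure from the protocol. It gives up Part A model-based comparisons, which the opening of SAP 10.2 already rules out.
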